5.3.2. Hospitalization

Patients at higher risk for TLS (any lymph node \geq 8 cm and/or circulating lymphoma cells) must be hospitalized for the initial dose of study drugs. Hospitalization should also be considered for patients with creatinine clearance $<$ 80 mL/min, in discussion with the study chair, [name]. Hospitalization will begin the evening prior to the first dose of study drugs and continue for 24 hours after. Upon admission, serum chemistry and hematology laboratory samples should be drawn, and IV hydration should be started with a target of 150-200 cc/hr or as clinically appropriate. Laboratory results should be reviewed, and electrolyte values should not demonstrate clinically significant abnormalities prior to the first dose of study drugs, or the patient should receive additional prophylactic treatment and hydration prior to the initiation of dosing. A nephrologist (or acute dialysis service) must be consulted/contracted on hospital admission (per institutional standards) to ensure emergency dialysis is available and the appropriate staff is aware and prepared to handle any necessary intervention for TLS. Telemetry should also be considered.

Serial vital sign assessments will be performed, and TLS laboratory samples will be drawn prior to the first dose of study drugs at 8, 12, and 24 hours post-dose, additionally, hematology samples will be drawn at 8 and 24 hours post-dose. These samples are to be immediately sent to the laboratory and the investigator or designee must promptly review the results. Laboratory values obtained prior to the dose of study drugs are to be used to determine whether a patient

developed a change related to TLS. Patients are still considered eligible to initiate therapy on Cycle 1 Day 1 if their hematologic parameters have dropped below eligibility requirements due to aggressive intravenous hydration. Laboratory results from the 24-hour post-dose sample must be reviewed prior to receiving the dose of study drugs for that day. Patients who develop electrolyte changes suggestive of TLS should undergo aggressive management and further monitoring per Appendix VII. Reintroduction of venetoclax in these patients should be performed as described in Section 5.3.1.

5.4. Pharmacokinetics

5.4.1. Objective

Steady-state plasma concentrations of ibrutinib, PCI-45227, and venetoclax after therapy administration will be determined on all patients enrolled during Phase I portion of the study on Cycle 1 Day 1.

5.4.2. Methods

Blood specimens for ibrutinib

Pharmacokinetic venous blood samples for ibrutinib (3 mL) will be collected pre- and post-administration (Section 5.4.3) in a green top tube. Blood specimens will be processed promptly, and plasma separated, frozen and stored. Plasma will be split into 2 cryovials (0.5 mL each). The tubes will be ultimately transported to Frontage Laboratories, Inc. See Appendix X for further details.

Frontage Laboratories, Inc.,

ATTENTION: [REDACTED]

Sample Coordinator

[name]

[name]

Blood specimens for venetoclax

The blood samples for venetoclax will be collected in 3 mL evacuated potassium EDTA (K2 EDTA)-containing collection tubes pre- and post-administration (Section 5.4.3). Sufficient blood will be collected to provide approximately 1 mL plasma from each sample. Immediately after collection, the blood samples will be inverted several times to ensure good mixing of the blood and anticoagulant, and will be placed in an ice bath or cryoblock until centrifuged. The blood samples for venetoclax will be centrifuged at approximately $1100 - 1600 \times g$ for 10 – 15 minutes using a refrigerated centrifuge (2° to 8°C) to separate the plasma within 1 hour of collection. The plasma samples will be transferred using plastic pipettes into screw-capped polypropylene tubes (Greiner # 122263-2DG) labeled with the drug name (Venetoclax), type of sample (plasma), the protocol number, the subject number, the study period and/or study day, and the planned

time of sampling relative to dosing. The plasma samples will be placed in a freezer within 2 hours of collection and maintained and at -20°C or colder until transferred to AbbVie.

Abbvie, Inc.

Attn: Sample Receiving
 [name]
 c/o: AbbVie Delivery Services
 [name]
 [name]

Measurement of plasma concentrations

Plasma concentrations of ibrutinib, PCI-45227, and venetoclax will be determined using validated liquid chromatography followed by tandem mass spectrometry (HPLC-MS/MS) methods.

Pharmacokinetic parameter estimation

The plasma concentration-time profiles will be analyzed using non-compartmental analysis. The following pharmacokinetic parameters will be calculated, whenever possible: area under the plasma concentration-time curve from time 0 to 24 hours (AUC(0-24)), area under the plasma concentration-time curve from time 0 to infinity (AUC(0-inf)), peak concentration (C_{max}), time to reach the maximum concentration (T_{max}), elimination half-life (T_{1/2}), accumulation factor R to the PK parameters (e.g., C_{max} and AUC), and metabolite-to-parent AUC ratio. Additional parameters including CL/F and V_d/F for ibrutinib may be calculated as appropriate.

5.4.3. Schedule

Table 3: Pharmacokinetic Sampling Schedule

Cycle	Day	Predose ^b	Time after ibrutinib and venetoclax dosing ^a			
			1h ± 15 min	2 h ± 15 min	4 h ± 30 min	6 h (± 1 h)
1	1	X	X	X	X	X
1	2	X				
1	15	X	X	X	X	X

a. Record actual time of sample collection.

a. Ibrutinib will be dosed at the same time as venetoclax.

b. Samples for ibrutinib and venetoclax on Cycle 1 Day 15 should be collected approximately 24 (± 2 h) hours after previous study dose and before administration of study drugs

Refer to the instructions on collecting and processing PK samples (Section 5.4.2.). On the day of the sampling visit, the clinical staff will instruct the subject to not take ibrutinib and venetoclax before arrival at the clinic. Study drug intake will be observed and recorded by clinic staff. The actual time (versus requested time) that each PK sample is drawn must be recorded in the using a 24-hour format.

6.2. Dose Modification for Adverse Reactions

The dose of study drugs should be modified according to the dose modification guidelines in Table 4 if any of the following toxicities occur:

- Grade ≥ 3 non-hematologic toxicity
- Grade 4 hematologic toxicity, except grade 4 neutropenia ≤ 7 days
- Grade 3 thrombocytopenia ($<50,000/\mu\text{L}$) in the presence of clinically significant bleeding
- Grade ≥ 3 neutropenia with infection or fever
- Grade 3 or 4 nausea, vomiting, or diarrhea if persistent, despite optimal anti-emetic and/or anti-diarrheal therapy.

For Grade 3 or 4 atrial fibrillation or persistent atrial fibrillation of any grade, consider the risks and benefits of ibrutinib treatment. If clinically indicated, the use of anticoagulants or antiplatelet agents may be considered for the thromboprophylaxis of atrial fibrillation. (See section 7.2.4)

If the dose of ibrutinib or venetoclax is reduced, at the investigator's discretion, the dose of ibrutinib or venetoclax may be re-escalated after 2 cycles of a dose reduction in the absence of a recurrence of the toxicity that led to the reduction. Dose changes must be recorded in the Dose Administration eCRF.

In patients with persistent and/or problematic Grade 1/2 non-hematologic adverse events such as fatigue, diarrhea, or nausea, the dose of study drugs can be reduced by one dose level at the discretion of the study investigator. The dose of study drugs may be re-escalated after 2 cycles of a dose reduction at discretion of the study investigator. If there is a recurrence of the prior toxicity, the patient will return to and remain on the lower dose. Dose changes must be recorded in the Dose Administration eCRF.

Table 4. Ibrutinib and Venetoclax Dose Modifications

Occurrence	Action to be Taken
First	Withhold study drugs until recovery to Grade \leq 1 or baseline; may restart at original dose level
Second	Withhold study drugs until recovery to Grade \leq 1 or baseline; Ibrutinib should be reduced by 140 mg per day and Venetoclax should be reduced by 100 mg
Third	Withhold study drugs until recovery to Grade \leq 1 or baseline; Ibrutinib should be reduced by 140 mg per day and Venetoclax should be reduced by 100 mg
Fourth	Discontinue study drug

****See Section 7 regarding permissible concomitant medications, include growth factor support and CYP3A inhibitors.**

6.2.1.1. Leukocytosis/Leukostasis

A high number of circulating malignant cells (>400,000/mcL) may confer increased risk of leukostasis; these subjects should be closely monitored. Administer supportive care such as hydration and/or leukapheresis as indicated. Ibrutinib may be temporarily held, and investigator should be contacted. Venetoclax should be continued in the setting of leukocytosis/leukostasis.

6.2.1.2. Dose Modification for Subjects with Hepatic Impairment

Subjects who develop acute hepatic toxicity with liver enzymes Grade 3 or higher while on study should be managed per standard dose modification guidelines in [Section Error! Reference source not found.](#) Ibrutinib is metabolized in the liver. In the population PK analysis (1,202 subjects), 179 subjects (14.9%) had mild hepatic impairment according to National Cancer Institute criteria and 12 subjects (1.0%) had moderate hepatic impairment. These subjects did not show a significantly higher ibrutinib exposure compared with subjects with normal hepatic function. In a hepatic impairment study, data showed an increase in ibrutinib exposure. For subjects with mild liver impairment (Child-Pugh class A), the recommended dose is 280mg daily. For subjects with moderate liver impairment (Child-Pugh class B), the recommended dose is 140mg daily. Monitor subjects for signs of ibrutinib toxicity and follow dose modification guidance as needed. It is not recommended to administer ibrutinib to subjects with severe hepatic impairment. Subjects with clinically significant chronic hepatic impairment at the time of

Screening (Child- Pugh class C) are excluded from study participation. Concomitant use of strong CYP inhibitors is not permitted in subjects with chronic hepatic impairment. Refer to Appendix D for Child-Pugh classification. Please refer to Table 3 for dose modifications due to hepatic impairment.

Table 5. Dose Modification Guidance for Hepatic Impaired Subjects

	Child Pugh class A (Mild hepatic impairment)*		Child Pugh Class B (Moderate hepatic impairment)**		Child Pugh class C (Severe hepatic impairment)
	Ongoing at time of enrollment	Develops during study	Ongoing at time of enrollment	Develops during study	Develops during study
Ibrutinib Dose (daily)	280 mg	280mg	140 mg	140 mg	Hold until improves to moderate [Class B] or better)

* If further reduction is needed due to non-hepatic toxicity, dose may be reduced to 140 mg. In the event that additional reduction is needed, ibrutinib should be held for non-hepatic toxicity until resolution.

** If further reduction is needed due to non-hepatic toxicity, ibrutinib should be held until resolution.

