	
• Concurrent systemic immunosuppressant therapy \leq 4 weeks of the first dose of study drug (e.g. cyclosporine A, tacrolimus, etc. or chronic administration of $>$ 20 mg day of prednisone or equivalent)• Known allergy to xanthine oxidase inhibitors and/or rasburicase for subjects at risk for tumor lysis syndrome• Infection requiring systemic treatment that was completed \leq14 days• Significant unresolved toxicities from prior anti-cancer therapy• Known bleeding disorders (e.g. von Willebrand's disease) or hemophilia.• History of stroke or intracranial hemorrhage within 6 months• Known history of HIV• Active hepatitis C or hepatitis B infection. Subjects who are positive for hepatitis B core antibody, hepatitis B surface antigen, or hepatitis C antibody must have a negative polymerase chain reaction (PCR) result before enrollment. Those who are PCR positive will be excluded.• Subjects with chronic liver disease with hepatic impairment Child-Pugh class B or C (See Appendix X)• Major surgery within 4 weeks of first dose of study drug.• Concomitant use of warfarin or other Vitamin K antagonists.• Subjects who received a strong cytochrome P450 (CYP) 3A inhibitor within 7 days prior to the first dose of ibrutinib or subjects who require continuous treatment with a strong CYP3A inhibitor (See Appendix VI)• Lactating or pregnant.• Current or history of graft versus host disease
--	---

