18. Any life-threatening illness, medical condition, or organ system dysfunction that, in the investigator's opinion, could compromise the subject's safety or put the study outcomes at undue risk.
19. Currently active, clinically significant cardiovascular disease, such as uncontrolled arrhythmia or Class 3 or 4 congestive heart failure as defined by the New York Heart Association Functional Classification; or a history of myocardial infarction, unstable angina, or acute coronary syndrome within 6 months prior to randomization.
20. Unable to swallow capsules or tablets or malabsorption syndrome, disease significantly affecting gastrointestinal function, or resection of the stomach or small bowel, symptomatic inflammatory bowel disease or ulcerative colitis, or partial or complete bowel obstruction.
21. Concomitant use of warfarin or other Vitamin K antagonists.
22. Subjects who received a strong cytochrome P450 (CYP) 3A inhibitor within 7 days prior to the first dose of ibrutinib or subjects who require continuous treatment with a strong CYP3A inhibitor (See Appendix VI)
23. High-grade transformation confirmed by biopsy.
24. Malabsorption syndrome or other condition precluding enteral route of administration.
25. Known CNS involvement by lymphoma

26. Erythema multiforme, toxic epidermal necrolysis, or Stevens-Johnson syndrome
27. Lactating or pregnant.
28. Unwilling or unable to participate in all required study evaluations and procedures.
29. Unable to understand the purpose and risks of the study and to provide a signed and dated informed consent form (ICF) and authorization to use protected health information (in accordance with national and local subject privacy regulations).
30. Currently active, clinically significant hepatic impairment (\geq moderate hepatic impairment according to the Child Pugh classification (class B or C)) (see Appendix X)

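### Section 6.2.1.2 and Table 5 treat Child-Pugh class B patients as eligible, while exclusion 30 and the synopsis bar them

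*Combined protocol and SAP*

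**What the plan says.** Four places bear on whether a patient with hepatic impairment may enter.

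- **Section 3.2, exclusion 30**, excludes currently active, clinically significant impairment, defined as at least "moderate hepatic impairment according to the Child Pugh classification (class B or C").
- **Synopsis, exclusion criteria**, excludes "Subjects with chronic liver disease with hepatic impairment Child-Pugh class B or C".
- **Section 6.2.1.2, text.** The sentence begins "Subjects with clinically significant chronic hepatic impairment at the time of" screening and ends, after naming Child-Pugh, with "class C) are excluded from study participation". Class B is not mentioned there as excluded. Earlier in the same paragraph: "For subjects with moderate liver impairment (Child-Pugh class B), the recommended dose is 140mg daily".
- **Section 6.2.1.2, Table 5.** Classes A and B each have two columns, one headed "Ongoing at time of enrollment" and one for impairment that develops on study. Class C has only the on-study column, with the instruction "Hold until improves to moderate [Class B] or better".

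**The concern.** A protocol should carry one entry rule for hepatic impairment. Here the eligibility section and the dosing section draw the line in different places, and the dosing section supplies a dose for a patient whom the eligibility section turns away. A site using Section 6.2.1.2 to decide how to start a patient with class B impairment would reasonably read it as permission to enrol at 140 mg.

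What is at stake is patient safety and consistent conduct across sites. Section 1.4.1 states that ibrutinib's safety has not been evaluated in patients with hepatic impairment. That statement covers every class, including class A, which the protocol admits, so it does not by itself justify a cut-off at class B. It does mean that whichever cut-off the sponsor has chosen should be stated once and applied everywhere. Table 5 also has a row for ibrutinib only, so a class B patient enrolled in error would have no venetoclax guidance from it. If, on the other hand, class B was meant to be eligible, exclusion 30 turns away patients the sponsor wants.

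**Working it through.** The check is a comparison of texts. No calculated figure in the plan is involved.

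**Step 1: status at entry, by class.**

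| Class at entry | Synopsis | Exclusion 30 | Section 6.2.1.2 sentence | Table 5, enrolment column |
|---|---|---|---|---|
| A | not excluded | not excluded | not excluded | 280 mg |
| B | excluded | excluded | not named as excluded | 140 mg |
| C | excluded | excluded | excluded | no such column |

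Classes A and C are handled the same way throughout. Only class B differs.

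**Step 2: is this an artefact of a broken table?** No. The sentence and the table layout agree with each other: class C is the only class named as excluded, and it is the only class without an enrolment column. Both follow from a rule that excludes class C alone, which is not the rule in Section 3.2.

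**Step 3: how much of Table 5 is affected?** Dose cells: class A 2 (280 mg at enrolment, 280 mg on study) + class B 2 (140 mg at enrolment, 140 mg on study) + class C 1 (hold, on study) = 5. Cells for a patient barred by exclusion 30: class B at enrolment, so 1 of 5. The class B on-study cell and the class C hold instruction are compatible with exclusion 30, which governs entry only.

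**Step 4: do other entry criteria make class B impossible anyway?** No. Section 3.1 limits bilirubin and PT/INR but sets no albumin limit, and it lists ascites among the indications for treatment. Using the Appendix X points, with bilirubin, INR and encephalopathy each scoring 1:

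- moderate to severe ascites (3) + albumin below 2.8 g/dL (3) + 1 + 1 + 1 = 9, class B
- mild ascites (2) + albumin 2.8 to 3.5 g/dL (2) + 1 + 1 + 1 = 7, class B

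So a patient can satisfy the laboratory limits and still score in the class B range of 7 to 9. Whether ascites in such a patient reflects liver disease or lymphoma is a clinical judgement, so the site needs a single clear rule.

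**Step 5: does any other section reconcile the two rules?** None was found.

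**Editorial, separate from the conflict.** The same paragraph sends the reader to Appendix D for the Child-Pugh classification and to Table 3 for the hepatic doses. The appendices are numbered in Roman numerals and the classification is in Appendix X. Table 3 is the pharmacokinetic sampling schedule (Section 5.4.3), and the hepatic dose table is Table 5.

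**The case against.** The strongest reply is that nobody should be enrolled wrongly. Section 3.2 requires that a patient meet none of the exclusions, the synopsis repeats the class B or C rule, and Section 14.2 has eligibility confirmed by the lead center's quality assurance office. Table 5 is dose guidance and does not confer eligibility. For a class B patient to enter, both the site and the central office would have to set aside a numbered exclusion in favour of a dosing table. This stands, and it is why the point is minor. It does not remove the conflict, since the central check works from a protocol that contains both rules.

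A second reply is that the Section 6.2.1.2 sentence is literally true, because class C is excluded under every version of the rule, and that it is merely incomplete. This is only partly right. Exclusion 30 and the Section 6.2.1.2 sentence both use the qualifier of clinically significant impairment, and each then says in parentheses which classes it covers: B or C in one, C alone in the other. Read together with the class B enrolment column, the sentence is a competing definition.

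A third reply is that the safety statement in Section 1.4.1 is not specific to class B. That is correct, and the conclusion does not depend on it. The wrong cross-references likewise have no bearing on class B eligibility.

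**Conclusion.** The inconsistency holds. The protocol excludes class B at entry in two places, and in Section 6.2.1.2 it both omits class B from the exclusion and gives it an enrolment dose. The extent is one sentence and 1 of 5 dose cells in Table 5. The response endpoint, the two-stage design, its sample size and its error rates are unaffected, and no estimate of excess exposure or harm is made. Weight: minor, on patient-safety grounds. Describing the enrolment cell as the error, and not exclusion 30, assumes that Section 3.2 expresses the sponsor's intent. That is the natural reading, because it is the governing eligibility section and the synopsis agrees with it.

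**What to change.** 1. In Section 6.2.1.2, change the parenthesis in the exclusion sentence from class C to class B or C.
2. In Table 5, delete the class B cell for impairment present at enrolment. Keep the class B on-study dose of 140 mg with its footnote, and the class C hold instruction. Four dose cells remain, none in conflict with exclusion 30.
3. As editorial corrections in the same paragraph, point to Appendix X for the Child-Pugh classification and to Table 5 for the doses.

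If the sponsor intends class B patients to be eligible, leave Section 6.2.1.2 and Table 5 on this point and amend exclusion 30 and the synopsis instead.

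The main option costs one sentence, one table cell and two cross-references. Neither option changes the statistical design or the analysis.

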7. CONCOMITANT MEDICATIONS/PROCEDURES

7.1. Permitted Concomitant Medications

Supportive medications in accordance with standard practice (such as for emesis, diarrhea, etc.) are permitted. Use of neutrophil growth factors (filgrastim and pegfilgrastim) or red blood cell growth factors (erythropoietin) is permitted while on therapy per institutional policy and in accordance with the ASCO guidelines. [31] Transfusions may be given in accordance with institutional policy.

Short courses (≤ 14 days) of steroid treatment for non-cancer related medical reasons (e.g., joint inflammation, asthma exacerbation, rash, antiemetic use and infusion reactions) at doses that do not exceed 100mg per day of prednisone or equivalent are permitted.

If clinically indicated, antimicrobial prophylaxis can be considered. Consider drug-drug interactions before initiating an agent. (Appendix V) Although there is a potential for drug-drug interactions, there is likely to be limited potential clinical effects, therefore Bactrim

(trimethoprim sulfamethoxazole) can be considered for Pneumocystis prophylaxis, with close clinical monitoring.

After consultation with the investigator the following may be considered; localized hormonal or bone sparing treatment for non-B-cell malignancies, and localized radiotherapy for medical conditions other than the underlying B-cell malignancies.

The following may be considered: localized hormonal or bone sparing treatment for non-B-cell malignancies, and localized radiotherapy for medical conditions other than the underlying B-cell malignancies.

Treatment for autoimmune cytopenias are permitted for <14 days at doses that do not exceed 100 mg per day of prednisone or equivalent.

7.2. Medications to be used with caution

7.2.1. CYP3A Inhibitors/Inducers

Ibrutinib is metabolized primarily by CYP3A4. Concomitant use of ibrutinib with drugs that strongly or moderately inhibit CYP3A can increase ibrutinib exposure, and strong CYP3A inhibitors should be avoided. Avoid grapefruit and Seville oranges during ibrutinib treatment as these contain moderate inhibitors of CYP3A. Dose adjustment of ibrutinib due to concomitant use of CYP3A inhibitors should follow Table 6.

Table 6. Ibrutinib Dose Modification Guidance for Co-Administration with CYP3A Inhibitors

Patient Population	Co-administered Drug	Recommended Ibrutinib Dose for the Duration of the Inhibitor Use ^a
B-Cell Malignancies	Mild CYP3A inhibitors	420 mg or 560 mg once daily per indication. No dose adjustment required.
	Moderate CYP3A inhibitors	280 mg once daily.
	Voriconazole 200mg twice daily Posaconazole suspension 100mg once daily, 100 mg twice daily, or 200 mg twice daily	140 mg once daily.
	Other strong CYP3A inhibitors Posaconazole at higher doses ^b	Avoid concomitant use and consider alternative with less CYP3A inhibitory potential. If these inhibitors will be used short-term (such as anti-infectives for seven days or less), interrupt ibrutinib. If the benefit outweighs the risk, and long-term dosing with a CYP3A inhibitor is required (more than seven days), reduce ibrutinib dose to 140 mg once daily for the duration of the inhibitor use.

^a. Monitor for adverse reactions to IMBRUVICA and interrupt or modify dose as recommended (see Dosage and Administration).

^b. Posaconazole at higher doses (posaconazole suspension 200 mg three times daily or 400 mg twice daily, posaconazole IV injection 300 mg once daily, posaconazole delayed-release tablets 300 mg once daily).

After discontinuation of a CYP3A inhibitor, resume previous dose of ibrutinib.

Avoid concomitant use of systemic strong CYP3A inducers (e.g., carbamazepine, rifampin, phenytoin, and St. John's Wort). Consider alternative agents with less CYP3A induction.

A list of common CYP3A inhibitors and inducers is provided in Appendix VI. For further information, please refer to the current version of the IB and examples of inhibitors, inducers, and substrates can be found at <http://medicine.iupui.edu/clinpharm/ddis/main-table/>. This website is continually revised and should be checked frequently for updates.

Venetoclax should be administered using caution with weak CYP3A4 inducers and inhibitors. If a moderate CYP3A inhibitor must be used, venetoclax should be dose reduced by at least 50%. Venetoclax can be resumed at the normal dose 3 days after discontinuance of the moderate CYP3A inhibitor.

This website is continually revised and should be checked frequently for updates. For the most comprehensive effect of CYP3A inhibitors or inducers on ibrutinib exposure, please refer to the current version of the IB.

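### The moderate-inhibitor row of Table 6 fixes ibrutinib at 280 mg with no cap at the current dose, so read literally it doubles the dose of a patient already at 140 mg

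*Combined protocol and SAP*

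**What the plan says.** Four sets of dosing rules in the combined protocol and SAP can apply to the same patient.

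- **Table 6 (Section 7.2.1).** The text says "Dose adjustment of ibrutinib due to concomitant use of CYP3A inhibitors should follow Table 6". The moderate-inhibitor row gives a single dose of 280 mg daily for as long as the inhibitor is used. The mild-inhibitor row reads "420 mg or 560 mg once daily per indication. No dose adjustment required". Once an inhibitor is stopped, the patient goes back to the earlier ibrutinib dose.
- **Table 4 (Section 6.2).** At the second and again at the third occurrence of a qualifying toxicity, "Ibrutinib should be reduced by 140 mg per day and Venetoclax should be reduced by 100 mg". Treatment stops at the fourth.
- **Re-escalation (Section 6.2).** A reduced dose "may be re-escalated after 2 cycles of a dose reduction in the absence of a recurrence of the toxicity" behind the cut, at the investigator's discretion.
- **Table 5 (Section 6.2.1.2).** The class A dose is 280 mg, and a footnote adds: "If further reduction is needed due to non-hepatic toxicity, dose may be reduced to 140 mg". The class B dose is set lower: "For subjects with moderate liver impairment (Child-Pugh class B), the recommended dose is 140mg daily".

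Neither Table 5 nor Table 6 limits its dose to the one the patient is already taking, and no sentence ranks the tables.

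**The concern.** Section 7.2.1 gives the reason for adjusting the dose: "Concomitant use of ibrutinib with drugs that strongly or moderately inhibit CYP3A can increase ibrutinib exposure". A table written to offset higher exposure should never raise the dose. The moderate row does so for one group, patients already at 140 mg.

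Those patients are at 140 mg because of toxicity or liver impairment. A site that follows Table 6 to the letter would double their ibrutinib while an inhibitor is being added. A site that follows Section 6.2 or Table 5 would stay at 140 mg. Two sites could therefore treat the same patient differently, each with protocol text behind it. Ibrutinib overexposure is a recognised issue in this trial: Section 5.2.1 says Dose Level 3 was abandoned because of raised ibrutinib exposure at Dose Level 2.

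**Working it through.** The plan gives no figure to reproduce here. The check is to list the doses a patient can be on and apply each rule.

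**1. Table 4 paths.** Starting doses come from Table 2 (420 mg at Dose Level 0; 560 mg at Dose Levels 1 and 2). The step is 140 mg at the second and third occurrences.

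- From 420 mg: 420, 420 - 140 = 280, 280 - 140 = 140, then discontinue.
- From 560 mg: 560, 560 - 140 = 420, 420 - 140 = 280, then discontinue.

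Table 4 alone therefore reaches 140 mg only from a 420 mg start.

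**2. The moderate row of Table 6 applied to each dose.** Change = (280 - current) / current.

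| Current dose | Table 6 dose | Change |
|---|---|---|
| 560 mg | 280 mg | -50% |
| 420 mg | 280 mg | -33% |
| 280 mg | 280 mg | 0% |
| 140 mg | 280 mg | +100% |

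**3. The rules side by side for a patient at 140 mg who starts a moderate inhibitor.**

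| How the patient came to 140 mg | Table 6 | Competing rule |
|---|---|---|
| 420 mg starter after the third Table 4 occurrence | 280 mg | Section 6.2: no increase until 2 cycles (2 x 28 = 56 days) have passed without recurrence |
| Class B impairment that developed on study (class B at entry is excluded by Section 3.2, criterion 30) | 280 mg | Table 5: 140 mg |
| Class A patient reduced under the Table 5 footnote | 280 mg | Footnote: 140 mg |

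In the first row the conflict disappears once 2 cycles have passed without recurrence. Table 6 footnote a (monitor, then interrupt or modify) and the similar advice in Section 6.2.1.2 do not say which rule prevails.

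**4. Illustrative exposure for the first row.** The documents give no fold increase for a moderate inhibitor, so a range F = 1.0 to 2.0 is assumed. If Table 6 is meant to restore exposure, it implies 420/280 = 1.5 or 560/280 = 2.0. Exposure is expressed relative to the 420 mg start without an inhibitor; before the inhibitor it is 140/420 = 0.33.

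| F | At 280 mg: 280F/420 | At 140 mg: 140F/420 |
|---|---|---|
| 1.0 | 0.67 | 0.33 |
| 1.5 | 1.00 | 0.50 |
| 2.0 | 1.33 | 0.67 |

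Under these assumptions, the toxicity reduction is fully cancelled at 280 mg once F reaches 1.5. The figures also assume dose-proportional exposure below 420 mg, whereas Section 1.4.1 supports proportionality only from 420 to 840 mg.

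**The case against.** The strongest reply is that nobody would read Table 6 as an order to increase. The section opens with the risk of higher exposure, the mild row presumes a patient on 420 or 560 mg, the long-term strong-inhibitor text speaks of reducing, and both tables are labelled as guidance. For the two liver routes, Table 5 or its footnote already supports 140 mg. This is right about intent, and many investigators would stay at 140 mg. It does not supply the missing cap or order of precedence.

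The second reply is reach, and it stands. Escalation had moved past Dose Level 0, which takes 3 or 6 patients plus any replacements. The phase II dose is not stated. The patient must also need a moderate inhibitor at the wrong moment. Appendix VI appears to list moderate inhibitors as prohibited, but that does not close the gap: Section 7.3 bars only the strong ones, and Section 7.2.1 gives ibrutinib and venetoclax doses for use with moderate ones.

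A reader might go further and infer that Table 5 is equally at fault, with a class A patient at 280 x 2.7 = 756 mg-equivalents, or 756/420 = 1.8 times starting exposure, using the AUC ratio in Section 1.4.1. The documents do not support that as a measure of this gap:

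- The figure follows from the 280 mg recommendation itself and applies equally to patients coming down from 420 or 560 mg.
- It rests on single-dose data, while the population analysis in Section 6.2.1.2 found no significantly higher exposure (graded by National Cancer Institute criteria rather than Child-Pugh).
- The class A footnote already supports 140 mg for non-hepatic toxicity, so only a residual gap remains in Table 5.

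**Conclusion.** The point holds as a narrow wording gap in the moderate-inhibitor row of Table 6. For a patient at 140 mg, the competing rules give 280 mg and 140 mg, and nothing in the protocol chooses between them. That difference of 140 mg (+100%) is the only firm magnitude. The exposure ratios are illustrative and depend on an assumed inhibitor effect and on dose proportionality outside the studied range.

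The number of patients affected cannot be derived from the documents but is likely very small. Any increase would end when the inhibitor stops, because the patient then returns to the earlier dose. It would be wrong to infer that the protocol means to raise doses, or that trial results are at risk: no sample size, error rate or analysis depends on this. It is a minor patient safety clarification.

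**What to change.** 1. In the moderate row of Table 6, write: *280 mg once daily, or the current dose if lower*. For consistency, do the same in the class A cells of Table 5.
2. Add one sentence: *where Tables 4, 5 and 6 give different ibrutinib doses, the lowest applies while those conditions last*. The closing words matter: without them the cap could hold a patient at 140 mg after class B impairment has improved to class A.
3. Keep the instruction to return to the earlier dose once a CYP3A inhibitor is stopped, and state that the Section 6.2 two-cycle rule covers only reductions made for toxicity. Sending every later increase through that rule would make a 560 mg patient without toxicity, lowered to 280 mg for a short inhibitor course, wait 56 days to resume.

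With the cap, a patient at 140 mg stays at 140 mg when a moderate inhibitor starts. The moderate-row dose does not change for patients at 280, 420 or 560 mg. The cost is amendment wording and a site memo.
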